3.4. Exploratory analysis

Additional exploratory endpoints as described below will be analyzed for further exploration of the ACP treatment effect with no multiplicity adjustment. Assessments will be done for Study Week 13 and Week 26 and the exploratory outcome measures are:

- Change from baseline in the dose and quantity of analgesic drugs used by the subject
- Change from Baseline in Quality of Life (QOL)
- Change from Baseline in Ankle Pressure
- Change from Baseline in Toe Pressure
- Proportion of subjects with an improvement in VAS pain score
- Change from baseline in Ulcer Size
- Difference on change from baseline in VAS pain score between the treated limb and the untreated limb if enough data are available for meaningful inference
- Difference on change from baseline in Ulcer Size between the treated limb and the untreated limb if enough data are available for meaningful inference
- Proportion of responders based on ulcer size, pain score and QOL, based on the following 3 criteria as described below

- Reduction in the last observed ulcer size by 50%
- Decrease in the last observed pain score by >2 or more
- Improvement of the last observed QOL total score by 20%

Alternatively, to account for unequal importance of ulcer size, QOL and pain score, the composite endpoint will be the hierarchical combination of the last observed ulcer size, the last observed pain score and the last observed QOL total score. We will calculate Win-Ratio using the [Finkelstein-Schoenfeld \(Finkelstein 1999\)](#) scoring algorithm detailed in the table. For each matched pair, the patient is labelled a “winner” or a “loser” depending on ulcer size. If that is not known, only then they are labelled a “winner” or “loser” depending on QOL and then pain score. Otherwise they are considered tied. The win ratio is the total number of winners divided by the total number of losers. A 95% confidence interval (CI) and P-value for the win ratio can be obtained. The Win-Ratio accounts for clinical priorities, so that ulcer size is considered more important than QOL and pain score and gets first priority. The method also recognizes that patients have differing risk profiles by using risk-matched pairs and provides an informative estimate of treatment difference with CI and P-value.

Scenario	Subject: i/j	Ulcer size	QOL total score	Pain score	Score
1	i	Large	not in consideration	not in consideration	-1
	j	Small	not in consideration	not in consideration	+1
2	i	Tied	Low	not in consideration	-1
	j	Tied	High	not in consideration	+1
3	i	Tied	Tied	High	-1
	j	Tied	Tied	Low	+1
4	i	Tied	Tied	Tied	+0
	j	Tied	Tied	Tied	+0

If i and j are reversed in severity than the value assigned to i is +1.

3.5. Safety analysis

All safety analyses will be performed in the Safety analysis set.

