#### 7.2. Visit 3: Treatment (Day 0)

Preparation of the subject for the treatment procedure will be initiated upon communication by Hemostemix's representative of the estimated date of the investigational product delivery.

If the batch is not released due to failure to meet release specifications, the subject will undergo a repeat Visit 2 within 21 days of the first Visit 2.

If the batch of IMP produced from the second blood also fails to meet specified release criteria, the subject will be withdrawn from the study.

The following clinical assessments will be performed just prior to the administration of the IMP.

- Physical examination, including Rutherford Assessment.
- Standard preoperative monitoring of heart rate, blood pressure, ECG, and body temperature.
- Assessment of ulcers including measurement of area in  $\text{cm}^2$  based on photography of lesions.

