### **16.2. Serious Adverse Event (SAE)**

Any untoward medical occurrence that at any dose:

- Results in death,

- Is life-threatening,
- Requires in-patient hospitalization ( $\geq 24$  hours) or prolongation of existing hospitalization,
- Results in persistent or significant disability/incapacity, or
- Is a congenital anomaly/birth defect.

All fatalities and serious adverse experiences (SAE), including serious clinical laboratory abnormalities even those that the investigator considers not to be related to the leg condition or the administration of the IMP must be immediately reported by phone, by email, or by fax to Hemostemix or its designee.

All significant symptoms and signs, which were not present at the previous visits, must be recorded as potential adverse experiences to be evaluated by the clinical investigator. Any medical condition present at the previous visits that remains unchanged or improves should not be recorded as an adverse experience at subsequent visits. However, if there is deterioration of a medical condition that was present at the initial visit, then this should also be considered a new adverse experience and reported.

If an SAE occurs, it will be noted and reported starting from the time point of the subject signing the Informed Consent Form, even if causality cannot be attributed to the IMP. AEs will be reported from Visit 2 onwards (time of blood draw for manufacture of the IMP).

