## **20.8. Safety Assessment**

Safety assessments, which will be performed for the Safety Analysis set only, will include the following:

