2. ANALYSIS SETS AND SUBGROUPS / TREATMENT GROUPS

2.1. Analysis sets

Intent-to-Treat (ITT) Analysis Set: The intent to treat (ITT) analysis set will consist of all subjects who have been randomized to the study. In accordance with the ITT principle, all subjects randomized will be kept in their originally assigned treatment group.

Modified Intent-to-Treat (mITT) Analysis Set: The mITT analysis set is a subset of the ITT analysis set. This set will consist of data from all subjects who have been randomized to the study and administered the IMP and had at least one treatment visit post IMP administration. This analysis set will serve as the primary analysis set for efficacy inference.

Per-Protocol (PP) Analysis Set: The per protocol (PP) analysis set is a subset of the mITT analysis set and will consist of all subjects with no major protocol violations that would be considered to impact the analysis of efficacy or safety.

Safety (ST) Analysis Set: The safety analysis set (ST) will consist of all subjects who have been randomized and received the Study IMP. This analysis set will be used as the primary set for safety inference.

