3.5.1. Adverse events

All adverse events will be coded using the Medical Dictionary for Regulatory Activities (MedDRA). Summaries will be presented for all adverse events (overall and by severity), adverse events determined by the investigator to be treatment-related (overall and by severity), serious adverse events, adverse events causing early termination and non-serious adverse events. The incidence of adverse events will be summarized using descriptive statistics by system organ class and preferred term. Subjects are counted only once in each system organ class category, and only once in each preferred term category. Treatment-related adverse event summaries will include adverse events with missing relationship to study drug. For the summaries by severity, subjects are counted at the greatest severity. Adverse events missing the flag indicating serious will be excluded from the summary of serious adverse events but included in the summary of non serious adverse events. Listings for deaths, serious adverse events, adverse events leading to discontinuation, MedDRA dictionary terms for adverse event descriptions, and adverse event preferred terms by subject number will be presented.

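### All safety tables and listings cover injected subjects only, although collection starts at consent or blood draw; events in never-injected subjects reach no safety output, and pre-injection events enter the per-arm AE rates

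*SAP*

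**What the plan says.** **Population for safety.** SAP 3.5 opens with "All safety analyses will be performed in the Safety analysis set". Protocol 20.8 is at least as strict: "Safety assessments, which will be performed for the Safety Analysis set only, will include the following". SAP 2.1 defines the set: "The safety analysis set (ST) will consist of all subjects who have been randomized and received the Study IMP". Protocol 20.5 has the same definition.

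**Outputs under that rule.** SAP 3.5.1 says "Summaries will be presented for all adverse events (overall and by severity"), and the same paragraph provides "Listings for deaths, serious adverse events, adverse events leading to discontinuation". The laboratory, vital-sign and ECG summaries (SAP 3.5.2 to 3.5.4) also fall under 3.5.

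**Start of collection.** Protocol 16.2 says of an SAE that "it will be noted and reported starting from the time point of the subject signing the Informed Consent Form", and for other events: "AEs will be reported from Visit 2 onwards (time of blood draw for manufacture of the IMP"). Visit 2 is scheduled at Day -7 ± 1.

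**Leaving before injection.** Protocol 7.2 allows one repeat of Visit 2 within 21 days of the first if the batch is not released, and then: "If the batch of IMP produced from the second blood also fails to meet specified release criteria, the subject will be withdrawn from the study". Protocol 7.2.1 also discontinues a subject who is unfit on the injection day.

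**The concern.** Collection starts before a subject can enter the set on which everything is reported. Two consequences follow.

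1. A subject may give blood once or twice, have an event, and never be injected. The event is collected, but no safety table or listing has a place for it, and this includes the death and SAE listings.
2. For subjects who are injected, the AE tables take all adverse events. Nothing restricts them to events that begin after injection, so an event of the blood draw or of the waiting period is counted under ACP-01 or placebo.

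Protocol 10.1.2 makes the safety of the intramuscular injection of ACP-01 a primary endpoint. The per-arm rates that answer it would include events that the injection cannot have caused. The blood draw is also a necessary step of an autologous product, and its harms have no table of their own. Protocol Appendix 1 (24.1) names anemia due to the draw, and nerve damage from blood collection, including by compression from a hematoma. Both are rated low probability.

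**Working it through.** The plan gives no figure to reproduce here. The check sets the rules side by side, then adds some arithmetic on scale.

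**Step 1. Can a never-injected subject reach a safety output?** Entry to the Safety set needs randomization and receipt of the IMP (SAP 2.1). All of SAP 3.5 runs on that set, and the listings sit inside 3.5.1. The answer is no.

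**Step 2. Is there another place?** The disposition table in SAP 3.2.1 counts randomized subjects by reason for early discontinuation, and AE/SAE and death are among the reasons. That gives a count without event term, severity or date. It also misses any event that did not end participation, such as a nerve injury at the draw in a subject later withdrawn for batch failure.

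**Step 3. Are these subjects randomized?** The documents do not settle this. Protocol 20.1 randomizes after eligibility is met and does not tie the step to the draw or to batch release. Two failed batches are also exclusion criterion H (Protocol 8.1.2), and screening ends only just before IMP administration (Protocol 7.1). A subject with two failed batches may therefore never be randomized, and would then be missing from the disposition counts too.

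**Step 4. Do pre-injection events of injected subjects enter the per-arm tables?** SAP 4.3 assigns a severity of mild to an AE that started before first dose and has no severity recorded, and uses the imputed value in the incidence summary. Pre-injection AEs are therefore in the summary by design. There is also a mismatch on causality. SAP 3.5.1 puts AEs with missing relationship into the treatment-related tables with no date limit, while SAP 4.4 imputes causality only for AEs starting on or after first dose. A pre-injection AE with missing relationship would be tabulated as treatment-related.

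**Step 5. Length of the pre-injection AE interval.**
- Single draw: Day -7 ± 1 gives 6 to 8 days.
- Repeat draw: 21 + 8 = up to 29 days from the first draw.
- Share of AE observation time for a subject followed to Day 365: 6/(365 + 6) = 1.6% to 8/(365 + 8) = 2.1%; with a repeat draw, 29/(365 + 29) = 7.4%.

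These are shares of time. The share of events would be the same only if events were spread evenly.

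**Step 6. How many subjects could be unreported?** The documents do not say. Take the 65 treated subjects in SAP 1.3 and assume that a fraction q of subjects with a draw were not injected. Then n0 = 65/(1 - q) - 65.
- q = 5%: 68.42 - 65 = 3.42, about 3.
- q = 15%: 76.47 - 65 = 11.47, about 11.

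Let p be an assumed risk of death or SAE between consent and planned injection. The chance that at least one such event goes unlisted is 1 - (1 - p)^n0:

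| n0 | p | Expected events | Chance of at least one |
|---|---|---|---|
| 5 | 1% | 0.05 | 4.9% |
| 5 | 5% | 0.25 | 22.6% |
| 10 | 1% | 0.10 | 9.6% |
| 10 | 5% | 0.50 | 40.1% |

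Both q and p are assumptions. The table shows only that the gap need not be empty.

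**The case against.** The case for leaving the plan alone has several parts.

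- **The endpoint is the safety of the injection, and injected subjects are its natural population.** This is right. It supports keeping the Safety set for the arm comparison. It does not support counting pre-injection events in that comparison, or leaving collected deaths and SAEs unlisted.
- **Nothing is hidden.** A reader might infer that these events appear nowhere at all. The documents do not support that. SAP 3.2.1 gives a reason count for randomized subjects, Protocol 16.2 and 16.5 send deaths and SAEs to the sponsor, and Protocol 17 gives the DSMB all accumulated data. But sponsor reporting and DSMB review are oversight during the trial, and a reason count is not a safety listing.
- **Subjects with two failed batches may be screen failures.** If so, leaving them out of by-arm tables is ordinary practice. A listing is still missing.
- **The arm comparison is not biased.** A reader might infer that it is. Protocol 7 and 12.4 show that placebo subjects also give blood, so draw-related events are expected in both arms, and pooling mainly dilutes the contrast. An all-causality table also does not attribute an event to the product, and the relationship categories in Protocol 16.3 from possible upward refer to timing after injection or to a known ACP response. This stands, except for events with missing relationship.
- **The split can be programmed later from onset dates.** This is true, and it is why the change is cheap. It is better fixed in the plan than chosen after the data are seen.
- **A date split will not capture draw-related anemia.** This stands. The Protocol 14 schedule has no laboratory test between a single draw and injection, so such anemia would usually first be found at a post-injection test.

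**Conclusion.** The point holds as a reporting gap that should be closed. It rests on the text alone: safety outputs cover only randomized and injected subjects, collection begins at consent or at the draw, and no treatment-emergent rule exists. No efficacy result or decision rule is affected.

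The size is modest or unknown. The pre-injection interval is about 2% of a fully followed subject's AE observation time with one draw, and up to 7.4% with two. Acute draw-related events would be concentrated in it, so the effect on particular event terms could be larger. The count of 3 to 11 never-injected subjects depends wholly on the assumed 5% to 15%.

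Two further inferences should be avoided. The bleeding/hematoma entry in Protocol Appendix 1 (24.1 j) is not a draw risk: it refers to the 23-gauge needle and the injection sites, whereas Protocol 7.1.2 specifies a 16-gauge needle for the draw. Nor should a blood volume be attached to these subjects. Protocol 7.1.2 gives up to 500 ml and Protocol 12.4 about 250 ml, and those passages must be reconciled. The point does not depend on which applies.

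**What to change.** In SAP 3.5 and Protocol 20.8:

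(a) List all deaths and SAEs from consent, and all AEs from Visit 2, for every subject whether injected or not. Add one table of events from Visit 2 up to injection in all subjects who had a blood draw.

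(b) Keep the Safety set for the arm comparison. Define treatment-emergent as onset or worsening on or after IMP injection, and use that definition for the per-arm AE and treatment-related tables. Apply it to the missing-relationship rule as well, so that SAP 3.5.1 and 4.4 agree.

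**Cost.** Wording in two documents, plus one table and one listing from data already collected. Per-arm AE counts will fall slightly as pre-injection events move to their own table. The new table should not be presented as the full rate of blood-draw harm, because anemia first found at a post-injection laboratory test would still fall in the per-arm tables.

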3.5.1. Adverse events

All adverse events will be coded using the Medical Dictionary for Regulatory Activities (MedDRA). Summaries will be presented for all adverse events (overall and by severity), adverse events determined by the investigator to be treatment-related (overall and by severity), serious adverse events, adverse events causing early termination and non-serious adverse events. The incidence of adverse events will be summarized using descriptive statistics by system organ class and preferred term. Subjects are counted only once in each system organ class category, and only once in each preferred term category. Treatment-related adverse event summaries will include adverse events with missing relationship to study drug. For the summaries by severity, subjects are counted at the greatest severity. Adverse events missing the flag indicating serious will be excluded from the summary of serious adverse events but included in the summary of non serious adverse events. Listings for deaths, serious adverse events, adverse events leading to discontinuation, MedDRA dictionary terms for adverse event descriptions, and adverse event preferred terms by subject number will be presented.

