4.3. Missing Severity Assessment for Adverse Events

If severity is missing for an AE that started before the date of the first dose of IMP, an intensity of mild will be assigned. If severity is missing for an AE that started on or after the date of the first dose of IMP, a severity of severe will be assigned. The imputed values for severity assessment will be used for the incidence summary; the values will be shown as missing in the data listings.

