4.4. Missing Causal Relationship to Investigational Product for Adverse Events

If the causal relationship to the IMP is missing for an AE that started on or after the date of the first dose of IMP, a causality of yes will be assigned. The imputed values for causal relationship to randomized treatment will be used for the incidence summary; the values will be shown as missing in the data listings.

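### Adverse events with a blank seriousness flag are tabulated as non-serious, so any resulting error in an arm's SAE count is downward, whereas missing post-dose severity and causality go to the adverse side

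*SAP*

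**What the plan says.** Four rules in the SAP decide where an adverse event goes when one of its attributes is blank.

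- **Seriousness (SAP 3.5.1).** "Adverse events missing the flag indicating serious will be excluded from the summary of serious adverse events"; they are counted in the non-serious summary instead. Protocol 20.8.1 has the same sentence.
- **Severity (SAP 4.3).** For an event that "started on or after the date of the first dose of IMP, a severity of severe will be assigned". For one that "started before the date of the first dose of IMP, an intensity of mild will be assigned".
- **Causality (SAP 4.4).** For an event that "started on or after the date of the first dose of IMP, a causality of yes will be assigned".
- **Causality in the tables (SAP 3.5.1, same paragraph as the seriousness rule).** "Treatment-related adverse event summaries will include adverse events with missing relationship to study drug".

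SAP 4.3 and 4.4 both add that imputed values are used in the incidence summaries and shown as missing in the listings. SAP 4.3 to 4.6 contain no corresponding convention for seriousness.

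Three protocol sections bear on the point. Section 16.2 defines a serious event by its outcome, including death, life-threatening events and hospitalization of at least 24 hours. Section 16.4 grades severity from 1 to 5, with severe at 3, life threatening at 4 and death at 5. Section 10.1.2 lists the safety of the injection among the primary endpoints.

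**The concern.** The seriousness rule is a stated convention, so whatever is blank at lock will be handled by it. Of the three attributes, seriousness is the only one for which a blank in a post-dose event resolves to the more favourable category, and no reason is given. A post-dose event with all three fields blank would be tabulated as severe, related and non-serious.

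Severe and serious are different concepts, so that combination is not impossible in itself. What needs explaining is that the conventions point in opposite directions.

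The rule also looks only at the flag. Where the recorded grade already shows that the event is serious under section 16.2, the rule overrides that information. At stake is the SAE table of a small trial in which a single subject is visible in the percentages.

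**Working it through.** The plan gives no figure to reproduce. The check compares the rules, bounds the count and illustrates the scale.

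**1. Direction of each rule for a post-dose event**

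| Blank field | Where the event goes | Direction |
|---|---|---|
| Severity (SAP 4.3) | Severe | Adverse |
| Causality (SAP 4.4 and 3.5.1) | Related | Adverse |
| Seriousness (SAP 3.5.1) | Non-serious | Favourable |

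Two limits apply. Missing severity before the first dose is set to mild. Severe is grade 3 of 5, so even after dosing the severity rule is conservative but does not assign the highest grade.

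**2. Bound on the SAE count.** Within an arm, let S be the events flagged serious and m the events with a blank flag, and take the recorded flags as correct. The true number of SAEs lies in [S, S + m]. The plan reports S, the lower end. The error, S minus the true count, lies between -m and 0. It is zero if m = 0 or if none of the m events was truly serious.

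**3. Between-arm difference.** The error in ACP-01 minus placebo is the ACP-01 error minus the placebo error. Each is zero or negative, so the difference can be positive, negative or zero. The one-directional result holds within an arm only.

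**4. Conflict with the definition.** Section 16.2 makes death and life-threatening events serious. Section 16.4 records them as grades 5 and 4. An event with either grade and a blank flag meets the definition, yet SAP 3.5.1 sends it to the non-serious table.

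**5. Scale (illustration).** SAP 1.3 gives 65 evaluable subjects for the final analysis and SAP 1.2.2 gives 2:1 allocation. An exact split would be 65 × 2/3 = 43.3 and 65 × 1/3 = 21.7, or about 43 and 22. For subjects whose only serious event lacks the flag:

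- one subject: 1/43 = 2.3 points on ACP-01, or 1/22 = 4.5 points on placebo;
- three subjects in one arm: 3/43 = 7.0 points, or 3/22 = 13.6 points.

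SAP 1.3 also mentions about 8 further patients. With 65 + 8 = 73 subjects, the split is about 49:24 and one subject is worth 1/49 = 2.0 or 1/24 = 4.2 points.

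The condition on the subject matters because incidence counts subjects. A subject with another flagged SAE stays in the overall SAE row. That subject drops out of a system organ class or preferred term row only if no other flagged event falls in the same row.

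**The case against.** The best defence is that the rule may never operate. SAEs must be reported immediately under protocol 16.2, section 16.5 sets up an SAE Report form due within 24 hours and electronic capture, deaths are listed separately, and the DSMB receives all accumulated data. For an SAE to be lost, the flag must be blank although a report should exist.

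This is a good reason to expect few blanks, but it does not settle the matter. Neither document requires flags to be reconciled with SAE reports before tabulation. The written-form steps in section 16.5 name deaths and SAEs considered unrelated to the condition under study, so SAEs attributed to the limb disease are not clearly covered there. A separate listing of deaths does not correct an incidence table and does not cover hospitalizations or disability.

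A second objection is that counting every blank as serious replaces a downward error with an upward one. Protocol Appendix 1 expects injection-site discomfort or pain with high probability, and one such record with a blank flag would become an SAE. This stands. It is why reconciliation has to come first and imputation be confined to what remains.

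Three stronger readings are tempting, and the documents do not support them:

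- **SAE counts are in fact biased downward, or biased in favour of ACP-01.** That would need blanks at lock on truly serious events, and for the second claim more of them on ACP-01. The documents report no blanks and give no sign of differential missingness, and assessors are blinded.
- **The SAP otherwise imputes to the worst case throughout.** It does not, given the mild rule before dosing and grade 3 after it.
- **A primary test is compromised.** Section 10.1.2 lists safety as primary, but section 20.3 refers to one primary endpoint, SAP 3.3.1 states only an efficacy hypothesis, and the adverse event summaries are descriptive. No alpha or decision rule depends on the SAE count.

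**Conclusion.** The point holds as a one-directional tabulation rule that is inconsistent with the SAP's own post-dose conventions and, for grades 4 and 5, with the protocol's definition of serious. Any error it causes in an arm's SAE count is downward.

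Its actual size is unknown and may be nil. The shifts of 2.3 and 4.5 points rest on an assumed 43:22 split and on a subject with no other flagged SAE. The 65 comes from the efficacy power statement and is not a stated size for the Safety set. The sentence should be changed because it governs SAE reporting and the change is cheap; there is no evidence that SAEs have been lost.

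**What to change.** In SAP 3.5.1, replace the sentence on the missing flag with:

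> Missing seriousness flags will be resolved before database lock by query and by reconciliation with the SAE Report forms and the section 16.2 criteria (including AEs graded life threatening or death). For AEs starting on or after the first dose of IMP, any flag still missing will be counted as serious in the SAE summary and shown as missing in the listings, and the number so imputed will be reported by arm.

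Align protocol 20.8.1 at its next amendment. Section 11 requires ethics approval before a protocol change is implemented, so until then the SAP should state that it departs from that sentence.

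The post-dose limit follows the split already used in SAP 4.3 and 4.4. If the team wants the pre-dose case covered explicitly, one further clause can leave those unresolved records in the non-serious summary, in parallel with the mild grade in 4.3.

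The cost is a reconciliation step before lock, a small programming change and the protocol alignment. The downside is that the SAE count may be slightly overstated. Reporting the number imputed by arm lets a reader see by how much at most.
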